Individuals who satisfy the telephone pre-screening criteria will be invited to a comprehensive in-person screening session. These sessions will be conducted by the PI or trained research staff. Individuals will first undergo informed consent; the consent form will describe the necessary eligibility confirmation that takes place before proceeding with the full study. Consenting individuals will complete several self-report questionnaires, submit to an examination of their height, weight, and vital signs (blood pressure, heart rate, and temperature), and provide a blood sample to ensure eligibility per the study criteria. Participant will receive a hand held tablet and instructions on how to complete the daily questions via the tablet. Vital signs & blood draws will be taken by the CRU nursing staff, using standardized sterile techniques.

Once the blood test results are available from the UAB Hospital Lab they will be reviewed by the PI and study doctor to confirm eligibility. All eligible participants will be contacted by telephone by a member of the research staff. If a participant's test results do not meet eligibility criteria, the individual will be informed that they are ineligible to participate and asked to return the handheld tablet to the research team. Alternatively, potential participants will be given a self-addressed envelope to return the tablet if they are unwilling to return to the site.

Visit 2

Participants will return to the CRU or Campbell Hall after approximately 14 days following visit 1. At this visit, a member of the study team will conduct an open interview to review the daily at-home symptom reporting and general health since the first visit. Also at this time the study team will instruct the participants on how to take their study medication. The placebo will be purchased from a compounding pharmacy such as Double Oak Pharmacy in Birmingham, Alabama. The participants will receive their initial 5 weeks supply of medication, which is placebo (single-blind). Participants will not be told when they are taking placebo or DXM until the end of study. The participants will also continue to record their symptoms twice a day using the hand-held device throughout the duration of the study for the entire (~20 weeks).

Visit 3

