Approximately 5 weeks after visit 2, the participant will return to the CRU so the nursing staff can record their vital signs and discuss any adverse events. The study staff will review their at home daily symptoms and receive DXM for approximately the next 5 weeks.

Visit 4

Approximately 5 weeks after visit 3, the participant will return to the CRU so the nursing staff can record their vital signs and draw 20cc of blood. The blood will be analyzed by the UAB Hospital lab to monitor the participant's liver & renal function. Also, at this visit the research team will review daily at-home symptoms & any adverse events. If any participant has experienced serious/severe adverse events the participant will be terminated from the study as to ensure there is no increased harm to the participant. If no adverse events have

been experienced the participant will receive the next dose of DXM to take for 5 weeks, and continue the athome daily symptom review using the hand-held device.

Visit 5

Approximately 5 weeks after visit 4, the participant will return to the CRU so the nursing staff can record their vital signs and draw 20cc of blood. The blood will be analyzed by the UAB Hospital lab to monitor the participant's liver & renal function. Also, at this visit the research team will review daily at-home symptoms & any adverse events. If any participant has experienced serious/severe adverse events the participant will be terminated from the study as to ensure there is no increased harm to the participant. If no adverse events have been experienced the participant will receive the normal dose of DXM to take for 30 days and continue the at-home daily symptom review using the hand-held device.

Visit 6

Approximately Two weeks after visit 5 the participant will return to the CRU or Campbell Hall to turn in their handheld device and have their final interview with the research staff. At this visit, [name] will review daily symptoms and general health since visit 10 and un-blind the participant to which medications were received during the study.

A +/- 3 day study visit window will be implemented for all study visits to allow for reasonable flexibility in the participant's schedule as well as staff availability.

At any time throughout the study, if a participant reports feeling unwell or having any adverse events from any of the supplements, a review will be conducted by the PI and study doctor. If necessary, appropriate medical management will be provided.

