If any participant is terminated from participating in the study, they will be required to return the hand-held device and any unused medicine back to a member of the UAB research study staff.

Study Timeline

The participant will be involved approximately 20 weeks for the entire study; this includes the in person screening, daily symptom reporting which is 10 minutes per day or less, and study medication disbursement. All blood draws will be conducted at the CRU in Jefferson Towers. Study medication disbursement will occur at UAB Campbell Hall or CRU.

Week	Task	Visit		Money
1	Screening	V1	Blood Draw Screening Labs & assays	\$50
2	Baseline			
3	Baseline	V2		\$100.00
4	Placebo			
5	Placebo			
6	Placebo			
7	Placebo			
8	Placebo	V3		\$100.00
9	DXM			
10	DXM			
11	DXM			
12	DXM			

13	DXM	V4	Blood Draw Hepatic / Renal & Assays	\$100.00
14	DXM			
15	DXM			
16	DXM			
17	DXM			
18	DXM	V5	Blood Draw Hepatic / Renal & Assays	\$100.00
	Baseline no			
19	drug			
	Baseline no			
20	drug	V6	Blood for assays	\$100.00
			Total Compensation	\$550.00

Compensation

Participants will be compensated with cash at screening, and check or direct deposit at all remaining visit. Cash is necessary at the screening visit as it will allow for most exclusionary criterion to be detected. Participants can receive up to \$550 in compensation for completing the study:

- Visit 1 (in-person screening): \$50
- Visits 2-6: \$100

Biospecimens

Peripheral blood samples will be collected and appropriately processed by the Clinical Research Unit (CRU) staff.

Screening session protocol: A 21/23g needle will be used to collect a maximum of 60cc of blood into labeled blood collection tubes to conduct screening tests. This blood will be tested by the UAB Hospital Lab to ensure that the participant meets the study criteria. The screening tests will include: complete blood count, erythrocyte sedimentation rate, thyroid stimulating hormone, free thyroxine, c-reactive protein, antinuclear antibodies, rheumatoid factor, liver function tests, kidney function tests and human chorionic gonadotropin. The total amount of blood drawn per participant for all study visits is 120cc.

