Participants should not take Dextromethorphan (DXM) if they have been diagnosed with phenylketonuria (PKU) because it could contain phenylalanine, if they are currently using or have used an MAO inhibitor, or if they have one of the following conditions: chronic bronchitis, emphysema, asthma, diabetes, liver disease, and mucus with cough or slowed breathing. These will be reviewed at the during the phone screen, in person screening and throughout the study. Dextromethorphan is known to produce side effects in individuals which include: slight drowsiness / dizziness, nausea or vomiting. Rarely, severe drowsiness can occur, participants will be instructed to notify study staff if they experience any of these side effects.

Grapefruit juice interacts with Dextromethorphan, participants will be asked to not drink grapefruit juice for the duration of the study.

Dextromethorphan is known to produce side effects in individuals which include: diarrhea, dizziness, cough, vomiting, swelling in the hands, ankles and or feet. Rarely slight drowsiness can occur; participants will be instructed to notify study staff if they experience any of these side effects. The most severe possible complication is serotonin toxicity.

The participant may experience some discomfort, bruising and the possibility of infection at the site of the blood draw on visits 1,3,6,9. Bruising should be minimal and should go away with a 2-3 days of the blood draw. We will minimize these risks by having only certified nurses or trained phlebotomist conduct the blood draws using standard sterile techniques.

The risks associated with taking the study medications can be primarily be avoided through proper screening of the participant and having a clear understanding of the medication the participant takes, educating the participant to contact the study staff of any and all changes to their medication. If an adverse event or side effect arises, a determination of severity and proper medical care will be advised and depending on the severity of the symptom the participant would be removed from the study and an evaluation of how to continue would be made by the study staff.

Minimization of Risks

Our screening procedures will minimize the probability of enrolling a patient who has a greater than normal risk of suffering adverse events from the medication (DXM). Any remaining risks for adverse events will be reduced by several checks:

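### The protocol ends study participation, not only study drug, after a serious or severe event, and specifies no visit, laboratory test or outcome record afterwards

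*Protocol*

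**What the plan says.** The relevant statements are spread over several Protocol sections.

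- **Visit 4 and Visit 5:** "If any participant has experienced serious/severe adverse events the participant will be terminated from the study as to ensure there is no increased harm". Both visits include vital signs, a blood draw for liver and renal function, and an adverse-event review. Further drug and continued diary entry are described for participants without adverse events.
- **Risks:** for an event or side effect at any time, "depending on the severity of the symptom the participant would be removed from the study". The sentence goes on to provide for "an evaluation" in these terms: "the participant would be removed from the study and an evaluation of how to continue would be made by the study staff".
- **End of Visit 6:** for a participant who at any time reports feeling unwell or "having any adverse events from any of the supplements, a review will be conducted by the PI and study doctor". It adds: "If necessary, appropriate medical management will be provided".
- **Just before Study Timeline:** "If any participant is terminated from participating in the study, they will be required to return the hand-held device and any unused medicine".
- **Visit 2:** participants "record their symptoms twice a day using the hand-held device throughout the duration of the study".

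Neither document describes an early-termination visit, an interview or laboratory test after termination, or a record of how the event ended.

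**The concern.** The plan treats stopping the study drug and leaving the study as one act. The stated reason for termination is to prevent further harm to the participant. Yet Minimization of Risks names the visit interviews and the liver and kidney tests among the checks that reduce risk, and termination takes the remaining scheduled ones away from the person who has just had a serious or severe event.

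What is at stake is the safety record. Whether such an event resolved, and how long it lasted, need not appear anywhere in the trial data. With 15 participants, each one affected is 1/15 = 6.7% of the sample, so one missing outcome matters to any summary of tolerability.

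**Working it through.** The plan gives no figure to reproduce on this point. The check counts what the Study Timeline still has scheduled after each possible point of removal.

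**Inputs (Protocol, Study Timeline and Study Visits)**
- Phases: 3 weeks screening and baseline + 5 placebo + 10 DXM + 2 without drug = 20 weeks, which matches the stated length of about 20 weeks.
- Visit 3 falls at week 8, Visit 4 at week 13, Visit 5 at week 18 and Visit 6 at week 20, each with a window of 3 days either way.
- On-drug liver/renal draws: Visits 4 and 5. The table lists Visit 6 blood for assays only, and Biospecimens describes the drug-phase assays as cytokine levels.
- Sample size: 15.

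**Diary weeks lost = 20 − week of removal**

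| Removal | Diary weeks lost | Reviews or interviews lost | Scheduled liver/renal draws lost |
|---|---|---|---|
| Soon after Visit 3 | up to 20 − 8 = 12 | Visits 4, 5, 6 | 2 (Visits 4 and 5) |
| At Visit 4 | 20 − 13 = 7 | Visits 5, 6 | 1 (Visit 5) |
| At Visit 5 | 20 − 18 = 2 | Visit 6 | 0 |

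**Which text permits each row.** The Visit 4 and Visit 5 rows follow from the explicit termination rule at those visits. The first row rests on the Risks section alone. The any-time clause at the end of Visit 6 provides review and medical management, not removal.

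**Dependence on the draw schedule.** Risks and Minimization of Risks place blood draws at visits 1, 3, 6 and 9, and the latter ties them to liver and kidney monitoring. Study Visits and Study Timeline describe six visits, with draws at 1, 4, 5 and 6. The table above uses Study Visits and Study Timeline. If a liver and kidney test were really due at Visit 6, removal at Visit 5 would lose one. The sections must be reconciled.

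**How likely the rule is to be used.** The documents give no event rate. If each participant independently has probability p of termination, the chance of at least one among 15 is 1 − (1 − p)^15. For assumed p of 1%, 2%, 5% and 10%, this is 14%, 26%, 54% and 79%.

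**Side effect on efficacy data.** The SAP's primary comparison uses the final four weeks of each treatment. If for DXM that means weeks 15 to 18, removal at Visit 4 loses all four and removal at Visit 5 loses none. The SAP states no handling for this. The safety point does not depend on it.

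**The case against.** The strongest case on the other side is that the documents are silent about later follow-up but do not exclude it. A reader might infer that participants with the worst events get no later interview, blood test or contact. The text does not support that: it promises review by the PI and study doctor, medical care and a staff evaluation. It sets no deadline for returning the device, and the consent form, which could hold follow-up terms, is not among the documents reviewed. This stands as a limit on the claim. It does not close the gap, because none of these provisions has a schedule, content or data-collection requirement.

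Three further limits also stand.

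- At Visits 4 and 5 the adverse-event review and liver/renal draw belong to the same visit at which termination is decided, so data around the event are not all lost.
- A reader might count Visit 6 blood as a lost safety test, making two draws lost at Visit 4 and three after Visit 3. The timeline lists that blood for assays, so the liver/renal counts are one and two.
- The diary is not shown to be a safety instrument. The SAP analyzes daily self-reports as efficacy outcomes, while adverse events are collected at visits. Its loss is a loss of observation, but mainly of efficacy data.

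Finally, termination after a severe event is a deliberate protective choice with a stated reason. This point does not question it. Protecting the participant from further drug does not require ending her observation.

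**Conclusion.** The concern holds in this form: a serious or severe event ends study participation, device return ends the diary, and the documents specify no assessment or outcome record afterwards.

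The firm losses are about 7 diary weeks, two reviews and one liver/renal draw for removal at Visit 4, and about 2 weeks and the final interview for removal at Visit 5. The larger loss soon after Visit 3 (up to about 12 weeks and both on-drug liver/renal draws) depends on the severity clause in Risks. All draw counts assume that Study Visits and Study Timeline, not the visit list in Risks and Minimization of Risks, give the true schedule.

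How many participants would be affected cannot be known from the documents. The conclusion concerns missing planned data collection. It is not a finding that care would be withheld, nor a view on which events should lead to stopping.

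**What to change.** In Visits 4 and 5, in the device-return sentence before Study Timeline, and in Risks, distinguish stopping study drug from leaving the study. State that a participant who stops drug returns unused medicine but, with her agreement, keeps the device and attends the remaining scheduled visits, with their planned assessments, through Visit 6. State that the event's outcome is recorded.

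Reconcile termination from the study with the staff evaluation promised in Risks, and reconcile the draw list at visits 1, 3, 6 and 9 with Study Visits and Study Timeline. Add a sentence to the SAP on how diary days after drug is stopped are classified. Which events lead to stopping, and how they are managed, remain with the sponsor.

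The cost is mainly wording in the protocol, the consent form and the SAP. The visits, draws and payments concerned are already in the per-participant schedule; recording the outcome is a small addition. The downside is a modest burden on the few participants who stop, some of whom may decline.

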 - iii. Short-term memory or concentration impairment;
 - iv. Muscle pain;
 - v. Joint pain without swelling or redness;
 - vi. Headaches of a new type/pattern/severity;
 - vii. Lymph node tenderness;
 - viii. Frequent or recurring sore throat
- 3. FM symptoms for \geq 12 months;
- 4. Participant completes daily self-report during the baseline period;

5. Able to attend UAB for all scheduled appointments.

Exclusion Criteria

- 1. Blood draw contraindicated or otherwise not able to be performed;
- 2. High-sensitivity c-reactive protein (HS-CRP) \geq 10 mg/L;
- 3. Erythrocyte sedimentation rate (ESR) >60 mm/hr;
- 4. Positive rheumatoid factor;
- 5. Positive anti-nuclear antibody (ANA);
- 6. Levels of thyroid stimulating hormone or free thyroxine outside UAB lab reference values;
- 7. Diagnosed rheumatologic or auto-immune condition;
- 8. Blood or Clotting disorder;
- 9. Use of blood thinning medication;
- 10. Current use of MAOI
- 11. Daily Consumption of grapefruit juice
- 12. Oral temperature >100°F at baseline;
- 13. Febrile illness or use of antibiotics in the 4 weeks before study commencement;
- 14. Planned surgery or procedures during the study period, or operated on in the 4 weeks before study commencement;
- 15. Pregnant or planning on becoming pregnant within 6 months; or currently breastfeeding
- 16. Regular use of any anti-inflammatory medication (such as aspirin, ibuprofen, naproxen);
- 17. Significant psychological comorbidity that in the discretion of the investigator compromises study integrity and/or a baseline HADS depression subscale score of ≥16;
- 18. Current litigation or worker's compensation claim;
- 19. Current participation in another treatment trial;
- 20. Planned vaccination during the study period, or vaccinated in the 4 weeks before study commencement.

Recruitment

FM participants will be primarily identified from a database of past research participants in our lab. All such participants have provided permission and expressed interest in being contacted for future studies. Individuals will also be drawn from the local community around Birmingham via referrals from local physicians or from online advertisements.

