 The risks associated with the blood draw will be minimized by using trained and licensed CRU nursing staff to perform the blood draw. Standard sterilization procedures will be followed to minimize the risk of infection. The blood draw site will be examined carefully to ensure no adverse events have occurred, and it is safe to proceed.

- 2. A more thorough investigation of adverse events will be collected at each laboratory visit. This includes a qualitative open interview assessment of symptoms and general health during the preceding month.
- 3. Also, blood tests will be collected at the mid-point of each treatment condition (visits 1, 3, 6, 9) to monitor liver and kidney function.
- 4. The relatively short duration of each study medication treatment (10 weeks)
- 5. Participants will be explained the symptoms of serotonin syndrome/ toxicity and will be instructed to report to the study staff if any symptoms occur. Also, individuals that have experienced an allergic reaction to any of the medication used in this study will be excluded from participating during the prescreening or at Visit 1.

Procedures to Maintain Confidentiality

Name, contact information, and medical history (participant reported –no medical records) are required to assess safety and eligibility for the study. Personally identifying information will also be collected as an identification requirement for study procedures. Identifying information will be stored on a single computer that is encrypted, and password protected at both operating system levels, and at the file level. All data maintained on paper-based records will be locked in a file cabinet in a locked room in the lab of the PI accessible only to the research study team.

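### The numbered exclusions omit past MAO inhibitor use and other reasons the risk sections give for not taking DXM, and the liver and kidney test visits those sections list do not match the six-visit schedule

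*Protocol*

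**What the plan says.** **Eligibility.** The protocol's Exclusion Criteria section has 20 numbered items. Item 10 is "Current use of MAOI". The Risks section goes further: DXM should not be taken "if they are currently using or have used an MAO inhibitor", with no time window. It gives the same warning for diagnosed phenylketonuria (PKU) and for "chronic bronchitis, emphysema, asthma, diabetes, liver disease, and mucus with cough or slowed breathing". It then says of the whole list: "These will be reviewed at the during the phone screen, in person screening and throughout the study". Minimization of Risks adds that "individuals that have experienced an allergic reaction to any of the medication used in this study will be excluded from participating", at prescreening or at Visit 1. Procedures to Maintain Confidentiality says that medical history is reported by the participant, without medical records.

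**Monitoring.** Risks puts blood draws at visits 1, 3, 6 and 9. Minimization of Risks gives the same four visits for liver and kidney tests and describes them as falling halfway through every treatment condition. The Study Visits section and the Study Timeline describe six visits. The Visit 6 text nevertheless refers back to a visit 10.

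**End of study.** The Visit 5 text supplies DXM for 30 days. The timeline shows weeks 19 and 20, after Visit 5, as weeks without drug. The timeline has assay blood at Visit 6. The Visit 6 text mentions no draw and allows either the CRU or Campbell Hall, whereas the Study Timeline section places every draw at the CRU.

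**The concern.** Staff who confirm eligibility need one list. If they work from the numbered exclusions alone, they can admit a past MAO inhibitor user, or someone with one of the other named conditions, whom the Risks section says should not take the drug. The protocol itself relies on proper screening as the main way to avoid medication risk, so the place where the screening rules are written matters.

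The safety section should also tell a reader, such as an ethics board member, when liver and kidney function is checked. As written it names a visit that does not exist and a visit with no draw, and it leaves out both visits at which the tests are scheduled during DXM treatment. The conflict over DXM after Visit 5 leaves open whether any drug is taken after the last liver and kidney test.

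**Working it through.** No figure in the plan has to be reproduced. The check sets the sections side by side and counts.

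**1. Eligibility items.** Risks names PKU plus six further conditions (counting mucus with cough or slowed breathing as one), which makes 7, and MAO inhibitor use: 7 + 1 = 8 items.

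- Of the 7 conditions, the 20 numbered exclusions name 0.
- MAO inhibitor use is covered in part: current use is listed, past use is not.
- The allergy exclusion under Minimization of Risks is not numbered either.
- Items wholly absent from the numbered list: 7 + 1 (allergy) = 8. Past MAO inhibitor use is a ninth gap.

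**2. Draw visits.**

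| Visit | Risk sections | Visit text | Timeline and Biospecimens |
|---|---|---|---|
| 1 | draw, liver/kidney | blood for eligibility, tests not named | week 1; liver and kidney tests among the screening tests |
| 2 | none | none | none |
| 3 | draw, liver/kidney | no draw | week 8; no draw |
| 4 | none | 20cc, liver/kidney | week 13; liver/kidney and assays |
| 5 | none | 20cc, liver/kidney | week 18; liver/kidney and assays |
| 6 | draw, liver/kidney | no draw | week 20; assay blood only |
| 9 | draw, liver/kidney | no such visit | no such visit |

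- Liver and kidney tests: {1, 3, 6, 9} against {1, 4, 5}. The overlap is {1}, so 1 of the 4 listed visits matches.
- All draws: {1, 3, 6, 9} against the timeline's {1, 4, 5, 6}. The overlap is {1, 6}, so 2 of 4 match.

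**3. Mid-points.** On the timeline, placebo runs over weeks 4 to 8 (middle: week 6, no visit) and DXM over weeks 9 to 18 (middle: end of week 13, which is Visit 4). The listed visits fall in week 1 (before treatment), week 8 (last placebo week) and week 20 (no drug), and the fourth does not exist. So 0 of 4 is at a mid-point. If the 30-day supply from Visit 5 is taken in full, DXM lasts 35 + 35 + 30 = 100 days with its middle at day 50. Visit 4, at about day 35, is then no longer the mid-point, and still no listed visit is.

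**4. After Visit 5.** Visit 6 follows Visit 5 by about 14 days. A 30-day supply covers those 14 days and 30 − 14 = 16 more. The timeline shows no drug in that interval. The last scheduled liver and kidney test is at Visit 5 on either reading.

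**The case against.** The strongest reply is that the rules are cumulative. Exclusion 10 is silent on past use and does not admit past users. Risks adds a stricter rule and says it is reviewed at the telephone screen, in person and throughout. This stands to the extent that no passage tells staff to enrol a past user. It does not remove the mismatch: someone can satisfy every numbered criterion and still be a person who, under Risks, should not take the drug.

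A reader might infer more than the documents support:

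- *That the unlisted conditions are not screened for.* Risks and Minimization of Risks say that they are.
- *That reliance on participant report is the defect.* Several numbered exclusions, such as litigation, planned surgery and grapefruit juice, also rest on report. Numbering the other items would not change how they are detected.
- *That kidney tests without a kidney criterion are a contradiction.* This is an omission at most. The Visit 1 text says that where a participant's "test results do not meet eligibility criteria, the individual will be informed that they are ineligible to participate", but the kidney test at Visit 1 may also serve as a safety baseline.
- *That liver and kidney function goes unmonitored on DXM.* Visits 4 and 5 carry the tests in both the visit text and the timeline.
- *That other sections confirm the Visit 6 draw.* Biospecimens has screening plus three draws, but assigns the three to the drug monitoring phase, while the timeline has Visit 6 off drug. The 120cc total leaves 120 − (60 + 20 + 20) = 20cc, but 60cc is a maximum and no Visit 6 volume is given. With one assay tube of 8 to 10cc the sum would be 108 to 110cc. Only the timeline shows this draw.
- *That the Visit 6 sample will be lost.* Holding the visit at the CRU satisfies both location statements. The risk arises only if Campbell Hall is used.

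**Conclusion.** The point holds as an internal inconsistency. Past MAO inhibitor use, seven conditions and prior allergic reaction are reasons not to take DXM, or to be excluded, that the numbered list does not carry. The safety section's list of liver and kidney test visits agrees with the schedule at 1 visit of 4, omits both on-drug test visits, and contains no treatment mid-point on either reading of DXM duration. The Visit 5 and Visit 6 texts each conflict with the timeline.

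The counts rest on treating mucus with cough or slowed breathing as one item, and on the Biospecimens list for liver and kidney tests at Visit 1, since the Visit 1 text does not name them.

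The primary analysis is not affected. The SAP models daily self-reported pain by condition, and neither the eligibility wording nor the laboratory visits enter that model. The Visit 5 conflict is raised here only for its bearing on safety testing. The issue should be corrected, but it does not put the trial's main result in doubt.

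**What to change.** - Reconcile Exclusion Criteria with Risks and Minimization of Risks so that a single eligibility list applies. It has to settle the two MAO inhibitor statements, the seven conditions and the allergy exclusion. The screening checklist should follow from it.
- Reconcile the visit numbers and the mid-point wording in Risks and Minimization of Risks, and the reference to visit 10 under Visit 6, with the visit descriptions, Study Timeline and Biospecimens.
- Reconcile the Visit 6 text and location with the draw shown in the timeline, and the DXM dispensing at Visit 5 with the drug-free weeks shown there.

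Which rule or schedule governs is for the investigators to decide. The SAP is written partly in the past tense. If enrolment is already complete, the investigators should record which eligibility rules and draw schedule were actually applied.

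The cost is protocol wording and a checklist. Some additional screen failures are possible against a target of 15 participants. The documents give no figure from which to estimate how many.
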